Appendix 3. Numerical Pain Rating Scale	38
Appendix 4. Intensive Care Delirium Screening Checklist	39
Appendix 5. Bliss Stool Scale Score	40
Appendix 6. Clinical Opioid Withdrawal Scale Score	41
Appendix 7. Childs Pugh Score	42
Appendix 8. Data and Safety Monitoring Board Charter	43
Appendix 9. Daily Nursing Bedside Data Collection Form	47
Appendix 10. Daily Investigative Team Data Collection Form	53
Appendix 11. Investigative Team Baseline Data Collection Form	57

Drug Substance: Movantik
Study Number: ESR-15-11000
Tufts IRB #12043
Version: Protocol version #19
Date: September 10, 2018

Abbreviations

Abbreviation	Explanation
APACHE	Acute Physiologic and Chronic Health Evaluation
COWS	Clinical Opioid Withdrawal Scale
CVP	Central venous pressure
DSMB	Data safety monitoring board
ECG	Electrocardiogram
FDA	Food and Drug Administration
GI	Gastrointestinal
ICDCSC	Intensive Care Delirium Screening Checklist
ICU	Intensive care unit
INR	International normalized ratio
IV	Intravenous
IRB	Institutional Review Board
LAR	Legally authorized representative
MC	Medical center
NRS	Numerical rating scale
OIC	Opioid induced constipation
PAMORA	Peripherally acting Mu opioid receptor antagonist
SAE	Serious adverse event
SAS	Sedation-Agitation Score
SBM	Spontaneous bowel movement
SOFA	Sequential organ failure assessment
WOCBP	Women of childbearing potential

Drug Substance: Movantik
Study Number: ESR-15-11000
Tufts IRB #12043
Version: Protocol version #19
Date: September 10, 2018

1. INTRODUCTION

1.1 Background

Among the more than 5 million adults who are admitted to an ICU each year in the USA, most receive IV opioid therapy. Overall, IV opioid use in critically ill adults is increasing given the greater awareness of untreated pain in this population and a recent level 1 recommendation in the Society of Critical Care Medicine's Pain, Agitation and Delirium Practice Guidelines for Critically Ill Adults that an analgesia-first (analgo-sedation) approach be used to optimize patient safety and comfort and improve tolerance with mechanical ventilator support [1]. In critically ill adults with acute respiratory distress syndrome, high-dose infusions of opioids are frequently used to depress respiratory drive and reduce oxygenation needs.

Paralysis of the lower gastrointestinal (GI) tract, defined as the inability to pass stool due to impaired peristalsis, is a common sequelae of opioid use in the critically ill. [2] As outlined in the 2012 recommendation's from the European Society of Intensive Care Medicine's Working Group for Defining Gastrointestinal Function in Intensive Care Patients, paralysis of the lower GI tract, defined as the absence of stool for 3 or more days, in the absence of mechanical GI obstruction, is the preferred terminology for opioid-associated bowel dysfunction rather than constipation given that the symptoms of constipation (e.g., painful defecation, abdominal pain, and a feeling of incomplete bowel evacuation) are not possible to evaluate in most patients in the ICU. Paralysis of the lower GI tract occurs in up to 72% of critically ill adults. [4-7]

The frequent use in the ICU of tube feed formulations having low fiber, a lack of patient mobility, and restrictive fluid policies will further magnify the impact of opioids on the prevalence of lower GI tract paralysis in this population. [8-12]. Lower GI tract paralysis will often lead to nausea and vomiting, aspiration, compromise the ability to administer enteral nutrition (and thus reach nutritional goals), greater abdominal pain, and has been shown to delay extubation. Constipation in the critically ill has recently been reported to be associated with greater delirium [13] One recent randomized study found that aggressive use of laxatives to prevent lower GI tract paralysis in critically ill adults was associated with lower daily organ dysfunction [as measured by the Sequential Organ Failure Assessment (SOFA) score][14] The lower GI tract paralysis that occurs in the critically ill often responds poorly to stimulant and osmotic laxative therapy. [10, 11]

1.2 Rationale for conducting this study

While stool softeners are routinely administered to patients on opioids, laxative-based bowel protocols are frequently not initiated in the ICU until signs of lower GI tract paralysis start to become evident. Even if laxatives were used earlier and more aggressively in the ICU care to prevent lower GI tract paralysis, a large proportion of patients receiving continuous IV opioid therapy would still not fully respond, and laxative-associated safety issues would increase. There is therefore an important unmet need for a safe and efficacious medication to prevent lower GI tract paralysis in critically ill adults who are initiated on IV opioid therapy. [10, 11]

Naloxegol, a pegylated naloxone tablet formulated for once daily oral administration, is a peripherally acting μ opioid receptor antagonist with established efficacy and safety in treating opioid-induced

Drug Substance: Movantik
 Study Number: ESR-15-11000
 Tufts IRB #12043
 Version: Protocol version #19
 Date: September 10, 2018

constipation (OIC) in non-ICU patients receiving scheduled moderate to high dose opioids for the treatment of chronic non-cancer pain. [10] Naloxegol has a mechanism of action, efficacy, convenience of administration, and safety profile that make it an ideal candidate for use as a preventative medication for lower GI tract paralysis in critically ill adults receiving continuous IV opioid therapy. A Phase II, proof of concept study to evaluate the efficacy and safety of naloxegol as a strategy to prevent lower GI tract paralysis in these high-risk critically ill adults, and to serve as a guide for future larger RCTs in this area, is crucial in filling a major knowledge and care gap in critical care practice.

Despite the prevalence of lower GI tract paralysis in the ICU, large knowledge gaps exist regarding its epidemiology, the optimal way to define it, and the ideal methods that should be used to characterize its severity and resolution. Moreover, the fact that no lower GI tract paralysis prevention strategy has ever been evaluated in the critically ill using a randomized, controlled design makes it unclear what a reasonable treatment effect should be and what the variability would be for any particular efficacy outcome that is chosen.

Therefore, while a strong rationale can be made that naloxegol may safely and effectively prevent lower GI tract paralysis in critically ill adults administered opioids, there is an important need for a rigorous Phase II proof of concept study to help justify and inform future research efforts with naloxegol in this population. Such a Phase II proof of concept investigation should be randomized and double-blind and carefully evaluate the validity and feasibility of the different endpoints that can be used to evaluate naloxegol safety and efficacy in the ICU patient at high risk for lower GI tract paralysis. This Phase II proof of concept investigation will allow for a much better characterization of how lower GI tract paralysis develops (and resolves) in the critically ill and also help define the variability that exists around each of the clinical endpoints that are evaluated. The recent finding that resolution of constipation will reduce organ dysfunction suggests that abdominal pressure monitoring may serve as an important secondary outcome in any study focused on evaluating the efficacy of a new intervention to reduce lower GI tract paralysis in critically ill adults. [14] This Phase II proof of concept study is critical in not only justifying the potential completion of larger investigations in this area but also to ensure, if they are justified, that they are correctly designed in terms of sample size, primary and secondary outcomes and how potential confounders are identified and managed. While larger investigations that have the power to evaluate important outcomes like nutrition delivery, delirium, use of early mobilization, duration of mechanical ventilation, length of ICU stay, ICU mortality and healthcare costs are critical when evaluating the true clinical benefit/impact of naloxegol as a lower GI tract paralysis prevention strategy in the critically ill, given the substantial time, effort and expense of conducting large multicenter studies in this area, it is critical that future research efforts be meticulously planned through thoughtful and rigorous Phase II proof of concept investigations like the one proposed.

1.3 Research hypothesis

Naloxegol will prevent lower GI tract paralysis in critically ill adults initiated on scheduled intravenous opioid therapy and its use will not lead to safety concerns.

1.4 Benefit/risk and ethical assessment

The package insert for naloxegol contains warnings that necessitate an assessment of the risk/benefit in the context of its planned use in this protocol.

Drug Substance: Movantik
Study Number: ESR-15-11000
Tufts IRB #12043
Version: Protocol version #19
Date: September 10, 2018

Potential Benefits

Lower GI tract paralysis occurs frequently in the ICU as a result of opioid initiation and is associated with substantial patient morbidity including discomfort, underfeeding, prolonged mechanical ventilation, delirium and potentially worsening organ dysfunction. The administration of currently available laxative(s) frequently does not prevent lower GI tract paralysis and thus there is a need for efficacious and safe therapies to prevent lower GI tract paralysis secondary to opioid use in critically ill adults. Naloxegol (Movantik) is new oral gut-selective Mu-receptor antagonist that is FDA-approved for the treatment of opioid-induced constipation in non-critically ill adults without cancer. In two large randomized controlled studies of patients with opioid-induced constipation (many of who were received one or more laxative treatments) it has been shown to be efficacious in quickly resolving opioid-induced constipation. If naloxegol is shown to be effective in preventing opioid-induced lower GI tract paralysis, it will represent an important advance in the care of the critically ill.

Potential Risks

- a. Naloxegol is contraindicated in patients with known or suspected gastrointestinal obstruction and patients at increased risk for recurrent obstruction due to potential for gastric perforation.

The following steps have been taken in the protocol to minimize the risk for this adverse event:
Patients with proven or suspected gastric obstruction are excluded from the study.

- b. Naloxegol is contraindicated in patients concomitantly taking strong CYP3A4 inhibitors (e. g., clarithromycin, ketcononazole) given the likelihood that the concomitant use of these agents will lead to supratherapeutic serum concentration (which could potentially induce opioid withdrawal).

The following steps have been taken in the protocol to minimize the risk for this adverse effect:
Patients taking a strong CYP3A4 inhibitor are excluded from the study. If there is a clinical need to use a strong CYP3A4 inhibitor medication (and another therapeutic option without these properties is not available) then the subject will be removed from the study.

- c. In the package insert, it is stated that naloxegol is contraindicated in patients concomitantly taking strong CYP3A4 inducers (e.g. rifampin, carbamazepine, St. John's Wort) as it could significantly decrease plasma naloxegol concentrations and may decrease the efficacy of naloxegol (Movantik).

The following steps have been taken in the protocol to minimize the risk for this effect. Patients taking a strong CYP3A4 inducer are excluded from the study. If there is a clinical need to use a strong CYP3A4 inducer medication (and another therapeutic option without these properties is not available) then the subject will be removed from the study.

- d. Cases of gastrointestinal perforation have been reported with the use of another peripherally acting mu opioid receptor antagonist (PAMORA) when used in patients who have a diffuse or local reduction in the structural integrity in the wall of the gastrointestinal tract.

The following steps have been taken in the protocol to minimize the risk for this adverse effect. The following patients are excluded from the study: i. admitted with an acute GI condition (e.g., clinical evidence of acute fecal impaction/complete obstruction, acute surgical abdomen, acute GI bleeding), ii. having a condition affect affecting GI motility or function (e.g. inflammatory bowel disease

Drug Substance: Movantik
Study Number: ESR-15-11000
Tufts IRB #12043
Version: Protocol version #19
Date: September 10, 2018

requiring immunosuppressive therapy, symptomatic Clostridium difficile, active diverticular disease, surgery on the colon or abdomen within 60 days of ICU admission or iii. having a history of constipation at the time of ICU admission.

- e. The effect of severe hepatic impairment (e.g. Cirrhosis with a Child-Pugh Class scale score of B or C) on the pharmacokinetics of naloxegol has not been evaluated.

The following steps have been taken in the protocol to minimize the risk for this adverse effect:
Patients with severe hepatic impairment are excluded from the study.

- f. Naloxegol has been very rarely associated with signs of opioid withdrawal.

The following steps have been taken in the protocol to minimize the risk for this adverse effect:

- i. Patients having an acute disruption of the blood brain barrier (that could potentiate naloxegol absorption to the CNS) are excluded from the study.
- ii. Patients taking scheduled opioids at the time of ICU admission are excluded.
- iii. Each study patient will be carefully monitored before and 2 hours each study dose for signs of opioid withdrawal using the Clinical Opioid Withdrawal Scale (COWS) score.

- g. No data regarding use of naloxegol in pregnancy and its use in a pregnant female taking opioids may precipitate opioid withdrawal in the infant.

The following step has been taken in the protocol to minimize the risk for this adverse effect. All female patients will be screened with a pregnancy test prior to study enrollment and if found to be pregnant will be excluded from the study.

- h. No data regarding use of naloxegol in lactating mothers and its use in a lactating female taking opioids may precipitate opioid withdrawal in the fetus.

The following step has been taken in the protocol to minimize the risk for this adverse effect. All lactating females will be excluded from the study.

- i. In the package insert, it is recommended that maintenance laxative therapy be discontinued before starting naloxegol and that laxative therapy should only be resumed in those patients who have OIC symptoms and after no sooner than 3 days after naloxegol was initiated.

This recommendation is based on the treatment of OIC in an outpatient setting and is not based on the usual clinical practices that are used to prevent lower GI tract paralysis in the ICU. Given that half the patients in the study will be randomized to placebo (in a blinded fashion), it is important that normal ICU lower GI tract paralysis prevention practices are incorporated into the research protocol. It is standard practice that all patients initiated on opioid therapy in the medical ICU at Tufts MC are started on scheduled docusate therapy and then managed with a step-wise laxative therapy (in a similar fashion to the laxative protocol developed for the study) as symptoms of lower GI tract paralysis develop and persist. The study laxative protocol accounts for patients who do have a SBM (i.e., laxative therapy is down-titrated/stopped), and stool softness and frequency is carefully being monitored as part of the study, so it is not expected that study patients, regardless of study

Drug Substance: Movantik
Study Number: ESR-15-11000
Tufts IRB #12043
Version: Protocol version #19
Date: September 10, 2018

assignment, will receive a greater amount of laxative therapy than is clinically necessary to prevent lower GI tract paralysis.

j. Scheduled use of opioids (≥ 100 mg morphine equivalents per day in the week prior to ICU admission) is a study exclusion criteria. This is information may be considered sensitive information and should be carefully collected in a de-identified fashion.

During the study screening process, the patient's medical record will be reviewed to see if the patient has a history of opioid use (both prescribed and non-prescribed). In addition, at the beginning of the consent discussion, the patient (legally authorized representative) will be asked whether the patient has used an opioid in the past week. If such use is not detected (i.e., through both methods), the patient will be deemed NOT to meet this study exclusion criteria. The study screening log (where the reason(s) for patient exclusion is documented) are completed de-identified so this information regarding opioid use will remain protected. If this opioid use history information is already documented in the patient record, then the patient will be excluded from study participation and the study team will never meet with the patient/authorized representative. If this opioid use history information is not documented in the patient record, but then identified through a discussion with the patient (or legally authorized representative), it will remain in the confidence of the investigative team (ie. not provided to the medical team) and documented in a de-identified fashion only on the study screening log as an exclusion criteria.

k. Removal of urinary (foley) catheters in the ICUs at Tufts MC is an important quality improvement initiative, will a urinary catheter be used solely for research purposes and is there a risk to inserting the bladder pressure transducer into a foley catheter that is already in place?

The answer is never. The bladder pressure that is being measured for research purposes requires that a bladder catheter be in place (to aseptically insert the bladder pressure transducer into the bladder catheter, thus creating a closed system). When the ICU team decides that a urinary catheter is no longer required for patient care then all bladder measuring will cease. If a subject is enrolled in the study who does not have a urinary catheter in place, a urinary catheter will NOT be inserted for research purposes. The study investigators met with the Tufts Med Center Urinary Tract Infection Committee chaired by [name], last fall to discuss two issues

1. The Tufts Medical Center Urinary Tract Infection Committee felt that the insertion of the pressure transducer into the red foly port (ie breaking the seal) would not lead to a clinically significant enough risk for a caUTI that would preclude abdominal pressure monitoring as part of the study.

Action: The investigators will raise the fact that there may be a very small risk for caUTI with abdominal pressure monitoring in the research protocol (in the risk/benefit portion) and will include a statement of this risk in the study ICF.

2. The Tufts Medical Center Urinary Tract Infection Committee was concerned that foley catheters may be left in place longer for abdominal pressure monitoring than would be clinically required (particularly given that ICU clinicians may sometimes "search" for an excuse to keep the foley catheter in place). [name] (on behalf of [name]) emphasized that there was no intent, on the part of the investigators, to keep a foley in place longer than was clinically necessary. In no instance, would a foley be inserted solely for abdominal pressure monitoring.

Drug Substance: Movantik
 Study Number: ESR-15-11000
 Tufts IRB #12043
 Version: Protocol version #19
 Date: September 10, 2018

The investigators will incorporate in the research protocol that MICU service will be formally asked each morning whether the foley catheter can come out of the patient (and to emphasize to the MICU team that a foley catheter should only remain in the patient if there is a clinical need). The answer to this question will be formally documented on the daily bedside study data collection form.

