4. SUBJECT SELECTION CRITERIA

The investigators will maintain a screening log for the duration of the study.

Each patient will meet all of the inclusion criteria and none of the exclusion criteria. A study screening sheet will be completed by a member of the investigative staff and confirmed by a second member of the investigation staff before randomization will occur.

All patients consecutively admitted to the medical ICU service who are admitted to the MICU, CCU, SICU or NCCU at Tufts Medical Center will be screened on a daily basis (through review of the ICU admission note, available laboratory data, the medication administration record, and the patient flowsheet by one of the study investigators who will determine if the patient meets all inclusion and exclusion criteria for participation in the study).

When the patient is found to meet all inclusion and no exclusion criteria, and Drs. [name], [name] or [name] have reviewed and signed the screening form, and the patient's primary ICU attending has approved their enrollment, the subject/legally authorized representative will be approached (either in person or by phone (ie. invited to come to Tufts MC to discuss the study) during the periods of 7am to 7pm.

4. 1. Inclusion criteria

- a. Admitted to the medical ICU service.
- b. Age \geq 18 years.
- c. Expected by the medical ICU attending physician to require admission to the MICU service for \geq 48 hours.
- d. Intravenous opioid administration in the prior 24 hours of \geq 100 mcg fentanyl equivalents (including both scheduled and "as needed" therapy).

Drug Substance: Movantik
Study Number: ESR-15-11000
Tufts IRB #12043
Version: Protocol version #19
Date: September 10, 2018

e. No objections from the MICU or attending physician for enrollment.

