4.2 Exclusion criteria

- a. Scheduled use of morphine, oxycodone, hydromorphone, fentanyl \geq 100 mg morphine equivalents per day in the week prior to ICU admission as evaluated by medical record review and/or interview with patient and/or family.
- b. Scheduled use of methadone at any dose in the week prior to ICU admission as evaluated by medical record review and/or interview with patient and/or family.
- c. History of constipation (as defined by the scheduled use of bisacodyl, senokot, lactulose, PEG 3350 (Miralax) and/or Fleet enema) prior to ICU admission as evaluated by medical record review and/or interview with patient and/or family.
- d. Current scheduled use a medication affecting gastric motility (i.e., metoclopramide, domperidone, erythromycin and loperamide).
- e. Current use of medication known to be a strong CYP3A4 inhibitor (itraconazole, lopinavir/ritonavir, clarithromycin, ritonavir, ketoconazole, indinavir/ritonavir, voriconazole, nefazodone).
- f. Current use of a medication known to be a strong CYP3A4 inducer (rifampin, carbamazepine, St. John's Wort).
- g. Known serious or severe hypersensitivity to naloxegol (Movantik) or any of its excipients.
- h. Patients admitted with a history of a neurologic condition that may affect the permeability of the blood-brain barrier (e.g. multiple sclerosis, recent brain injury, Alzheimer's disease, uncontrolled epilepsy, acute stroke, acute meningitis).
- i. Patients admitted with an acute GI condition (e.g., clinical evidence of acute fecal impaction/complete obstruction, acute surgical abdomen, acute GI bleeding).
- j. Patients with a condition affecting GI motility or function (e.g. inflammatory bowel disease requiring immunosuppressive therapy, symptomatic Clostridium difficile, active diverticular disease, surgery on the colon or abdomen within 60 days of ICU admission).
- k. Patients with underlying cancer who are at heightened risk of GI perforation such as those with underlying malignancies of the GI tract or peritoneum, recurrent or advanced ovarian cancer, vascular endothelial growth factor inhibitor treatment.
- l. Current use of total parenteral nutrition
- m. Administration of enteral nutrition through a jejunum tube.
- n. Severe hepatic dysfunction

Drug Substance: Movantik
Study Number: ESR-15-11000
Tufts IRB #12043
Version: Protocol version #19
Date: September 10, 2018

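### The protocol calls naloxegol contraindicated in patients at increased risk of recurrent GI obstruction, but no eligibility criterion explicitly excludes them

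*Protocol*

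**What the plan says.** Section 1.4 of the protocol lists risks from the package insert and, under each, the step taken to reduce it. Risk (a) reads "Naloxegol is contraindicated in patients with known or suspected gastrointestinal obstruction and patients at increased risk for recurrent obstruction", because of possible perforation. The step that follows is: "Patients with proven or suspected gastric obstruction are excluded from the study". Risks (b) and (c) concern strong CYP3A4 inhibitors and inducers. For inhibitors the step is "Patients taking a strong CYP3A4 inhibitor are excluded from the study", and the one for inducers is parallel.

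Eligibility is set in Section 4, which requires that "Each patient will meet all of the inclusion criteria and none of the exclusion criteria". Section 4.2 lists criteria (a) to (u). The two drug-interaction groups have their own lines: (e), "Current use of medication known to be a strong CYP3A4 inhibitor", and (f), "Current use of a medication known to be a strong CYP3A4 inducer". Obstruction is named once, in (i), as an example of an acute GI condition at admission.

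**The concern.** The protocol declares a group contraindicated and says that steps have been taken, but for the recurrence-risk group it states no step. Whether such a patient is kept out then depends on how a screener reads an open-ended criterion, or on an attending physician's objection.

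Entry is the right place to act, because re-obstruction would be hard to recognise later. Section 1.1 says that symptoms such as abdominal pain cannot be assessed in most ICU patients, and Section 5.2.1 expects about two-thirds of potential subjects to be ventilated. A re-obstructed patient who passes no stool looks like a case of the trial's own primary outcome and moves up the laxative steps of Appendix 1. Step 4 stops study drug but gives methylnaltrexone, which 4.2(q) lists with naloxegol as an opioid antagonist. Consultation with gastroenterology or surgery at that point is only to be considered.

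**Working it through.** No sample size, power or error rate is involved, so the check is a comparison of text plus a simple dose count.

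**Contraindicated groups in 1.4(a) to (c), traced to eligibility**

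| Group | Mitigation sentence in 1.4 | Line in 4.2 |
|---|---|---|
| Known or suspected GI obstruction | Yes, worded as gastric | (i), as an acute condition at admission |
| Increased risk of recurrent obstruction | None | None |
| Strong CYP3A4 inhibitor | Yes | (e) |
| Strong CYP3A4 inducer | Yes | (f) |

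Not carried over: 1 of 4.

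**Count of exclusion criteria.** (a) to (n) is 14 and (o) to (u) is 7; 14 + 7 = 21. Criteria naming earlier obstruction or recurrence risk: 0 of 21. The word recurrent appears only in (k), about ovarian cancer.

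**Partial cover.** On my reading, three criteria remove part of the group:

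- (c) "History of constipation (as defined by the scheduled use of bisacodyl, senokot, lactulose, PEG 3350 (Miralax) and/or Fleet enema"; this catches patients on scheduled laxatives.
- (j) conditions affecting GI motility or function. The examples include treated inflammatory bowel disease, active diverticular disease, and colonic or abdominal surgery within 60 days of ICU admission.
- (k) cancers with heightened perforation risk.

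Section 1.4(d), which deals with perforation directly, restates (i), (j) and (c) and adds nothing on recurrence.

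**Test case.** Take a patient with a resolved adhesive obstruction, surgery more than 60 days ago, no listed cancer and no scheduled laxative. Criteria (c) and (k) do not apply. The surgery example in (j) does not apply, and its time limit suggests that older surgery is acceptable. Criterion (i) does not apply without an acute condition at admission. The patient need not meet any exclusion.

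**Doses before the laxative guideline stops study drug, for a patient who passes no stool**

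- Stop point: Step 4, at 6 days from the start of scheduled opioid therapy (Appendix 1 and its footnote): 6 × 24 = 144 h.
- First dose: 0 to 72 h after the first IV opioid in the ICU (4.2(o)). I treat the two opioid clocks as the same, which is an assumption.
- Daily doses before the stop = (144 − time of first dose in hours) / 24.
- First dose at 72 h: (144 − 72) / 24 = 3 (at 72, 96 and 120 h).
- First dose at 0 h: (144 − 0) / 24 = 6 (at 0, 24, 48, 72, 96 and 120 h).

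The range is about 3 to 6 doses, unless a physician acts sooner. Six is a ceiling, since qualifying opioid use, consent and randomisation must all come before the first dose. A patient who does pass stool never reaches Step 4 and could receive up to the 10-day maximum.

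**The case against.** The best defence is that cover is wider than the single sentence in 1.4(a). Criterion (j) is introduced by examples, so a screener could apply it to a stricture or symptomatic adhesions. Section 1.4(d) adds perforation safeguards. A second team member confirms the screening sheet (Sections 4 and 5.3), the attending must approve enrollment before any approach for consent, and 4.1(e) requires "No objections from the MICU or attending physician for enrollment". The sheet itself is not in the documents and may already ask about earlier obstruction. The word gastric has little practical effect, because (i) governs eligibility and is not limited to the stomach. A resolved episode is also not the same as increased risk of recurrence, and a line that relies on the investigator's judgement keeps some of the discretion complained of. After dosing starts, study drug can be stopped for an adverse event (5.8.1, reason 1), at Step 4 (reason 2), or earlier at a physician's discretion (Section 5.6 and the note closing the adverse event reporting section).

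Much of this is fair, and it limits the size of the problem. It does not close the gap. A second check against criteria that omit the group cannot be relied on to exclude it. Attending approval carries no standard about obstruction, and none of the eight stopping reasons in 5.8.1 names obstruction. A line that makes the screener ask about recurrence risk is a real gain, even if the answer is a judgement: the contraindication is itself stated in terms of risk.

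**Conclusion.** The concern holds. One of the four groups that 1.4(a) to (c) call contraindicated was not carried into eligibility, and 0 of 21 criteria name it. The wording gap is certain. Its practical size is not: the documents give no frequency of earlier obstruction and do not include the screening sheet, so the number of patients at stake among 36 cannot be estimated and is probably small. No endpoint, analysis or power figure changes. The case for acting rests on the gravity of the named harm, the protocol's own statement of the contraindication, and the absence of any stated reason for including these patients. The 3-to-6-dose range applies only to a patient who passes no stool and rests on the single-clock assumption.

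**What to change.** Add one line to Section 4.2, for example: *GI obstruction at any level, established or suspected, or increased risk of recurrent obstruction in the investigator's judgement from the medical record and/or interview, with any history of bowel obstruction weighed in that judgement.* A resolved earlier episode then prompts a decision and does not exclude by itself.

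Put the same line on the enrollment screening sheet if it is not already there. In the mitigation sentence of 1.4(a), change gastric to gastrointestinal and add recurrence risk.

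The work is one criterion and one corrected sentence, and it uses the record review and interview that 4.2(a) to (c) already call for. The downside is the loss of a few otherwise eligible patients; the number cannot be worked out from the documents but is probably small.
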